Since the introduction of CAMBRA (CAries Management By Risk Assessment) in the Journal of the California Dental Association in 2007,^{8,9} the marketplace for anti-caries products has surged. As a result, many approaches to the management of dental caries have been introduced and dental practitioners and sales representatives have promoted several anti-caries products. In addition, the reduction or the abatement of the progression of dental caries (coronal, root and interproximal) as a result of a caries management program has been reported.^{10,11} Many caries management products have ingredients that include fluoride and calcium phosphate (Amorphous Calcium Phosphate-Casein Phosphopeptide (Recaldent™),¹² Tri-Calcium Phosphate™ or Novamin™).¹³

Moreover, encouraging clinical findings have been reported, including, but not limited to the reduction of white spot enamel lesions and dentinal hypersensitivity.¹⁴

The topical application of “antihypersensitivity” materials is a common recommendation (least invasive of the “standard of care” recommendations) to diminish dentinal hypersensitivity and will serve to provide data for the research study. The study will evaluate which of these products result in the greatest reduction of dentinal hypersensitivity. The application of the experimental products for the reduction of dentinal hypersensitivity is for research purposes.

The methods used to test sensitivity in this study have been used in published studies.^{6,15,16} The VAS scale used in this study has also been used for tooth sensitivity studies.^{16,17} A 30% decrease in VAS score has been shown to be clinically meaningful.^{18,19}

This pilot study would investigate the ability of anti-caries products to reduce dentinal hypersensitivity when compared to a sensitivity-reducing dentifrice. It would be a novel contribution to the dental community if a material that is proven to reduce tooth decay is also proven to reduce dentinal hypersensitivity. The results may potentially have a tremendous impact on the dental community because it may provide dental professionals a scientifically-supported approach to improve the comfort and quality of life of periodontal patients (patients who are treated for gum disease/ bone loss around teeth) and increase the lifespan of teeth that undergo periodontal treatment.

III) Research Plan

A) Experimental Design

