Each subject will be randomized to a treatment arm using a randomization website (www.random.org). When subjects have multiple teeth eligible for the study, a separate randomization scheme (also from www.random.org) will be used to select that tooth. A printout of the randomization scheme will be used by the investigator distributing the products.

Blinding

Examiners collecting the sensitivity data will be blinded as to which group the subject is in. An investigator who did not examine the subject will distribute the product.

C) Products

Group	Product 1	Product 2
Group I (Control)	Sensodyne (Potassium Nitrate) manufactured by GalaxoSmithKline	N/A
Group II	Crest Cavity Protection manufactured by Procter and Gamble	MI Paste Plus (CPP-ACP with fluoride) manufactured by GC America
Group III	Clinpro 5000 (5000ppm NaF with TCP) manufactured by 3M ESPE	N/A

Sensodyne is FDA approved for decreasing tooth sensitivity. It is approved for use as it is being used this study.

Clinpro 5000 has been FDA approved for the prevention or reduction of dental caries. A reduction in dentinal hypersensitivity has been anecdotally documented in the literature.

MI Paste Plus is FDA approved for the reduction of dentinal hypersensitivity. It is approved for use as it is being used this study.

Crest Cavity Protection Toothpaste is FDA approved as an anticavity drug.

Oral-B 35 soft manual toothbrush is FDA approved and being used as approved for this study.

All products are being used according to manufacturer's instructions.

D) Subject Characteristics

1) Inclusion Criteria

- At least 18 years of age
- Tooth with exposed root surface and/or exposed dentin
- Tooth with a VAS score greater than or equal to 3
- No adjacent tooth/teeth with sensitivity (as defined as greater than 2 on the VAS)

2) Exclusion Criteria

- Participation in another dental study that may alter the results of this study.
- A medical condition that could interfere with reliable pain reporting (e.g., pain disorders)
- Any chronic medical condition that requires the regular use of pain or anti-inflammatory medications
- Used a desensitizing dentifrice within the preceding four weeks
- Have received an antihypersensitivity treatment (varnish or precipitating solution) of the identified tooth within the preceding four weeks
- Undergoing active orthodontic treatment.

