Subjects will be instructed to brush twice daily (2 minutes each time in the morning and the evening) using Clinpro 5000 (5000ppm NaF with TCP).

The study team member will describe the proper use for the products and will review oral hygiene instructions. Once the subject demonstrates understanding for the use of the products, the products and a handout for the use of the products will be distributed. A toothbrush and 2-minute timer will also be given to the subject. The use of any other topical dental products (e.g., rinses, toothpastes, fluoride varnish) will be discontinued. The subjects may use additional products (e.g., dental floss, interproximal devices) to remove plaque. Subjects will be given a diary in which to track product usage. Diary is for research purposes.

Visit 2 (2 weeks +/- 2 days after Visit 1):

A study team member who did not examine the subject at the initial visit will ask the subject for any changes in the medical or dental history. The study team member will also discuss patient compliance, adverse events, review and collect the patient's diary, hand out a new patient diary, and answer any questions that the subject has regarding the products and dispense additional products, if necessary.

Eligibility and subject withdrawal criteria will be reviewed to ensure the subject still qualifies for the study.

The same examiner from the initial visit will then conduct the oral exam and collect the sensitivity data (if necessary, another examiner may see the subject, however, this will be avoided if possible).

An oral exam, including evaluation of oral cavity and soft tissues, will be completed following standard of care procedures.

The same sensitivity tests will be done as at Visit 1. Tests are for research purposes.

Visit 3 (4 weeks +/- 2 days after Visit 1):

A study team member who did not exam the subject at the initial visit will ask the subject for any changes in the medical or dental history. The study team member will also discuss patient compliance, adverse events, review and

collect the patient's diary, hand out a new patient diary, answer any questions that the subject has regarding the products.

Eligibility and subject withdrawal criteria will be reviewed to ensure the subject still qualifies for the study.

The same examiner from the initial visit will then conduct the oral exam and collect the sensitivity data (if necessary, another examiner may see the subject, however, this will be avoided if possible).

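### The four-week prior-use exclusion washes out users of the control type of product but, as worded, admits current Clinpro 5000 users and is ambiguous for MI Paste Plus; the effect on the comparison has unknown direction and size

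*Combined protocol and SAP*

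**What the plan says.** Section III.D.2 (Exclusion Criteria) has two rules on prior use. One excludes a person who "Used a desensitizing dentifrice within the preceding four weeks". The other excludes those who "Have received an antihypersensitivity treatment (varnish or precipitating solution) of the identified tooth within the preceding four weeks"; its bracket confines it to two kinds of treatment.

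Section III.C (Products) describes the three study products differently:

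- Control: "Sensodyne is FDA approved for decreasing tooth sensitivity".
- Clinpro 5000: "Clinpro 5000 has been FDA approved for the prevention or reduction of dental caries". On sensitivity it adds only: "A reduction in dentinal hypersensitivity has been anecdotally documented in the literature".
- MI Paste Plus: "MI Paste Plus is FDA approved for the reduction of dentinal hypersensitivity". Section III.F has it applied by finger after brushing with a separate toothpaste, and nowhere calls it a dentifrice.

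Section III.F (Study Procedures) makes Visit 1 both the screening and the baseline visit. At dispensing, after the baseline sensitivity tests, it states: "The use of any other topical dental products (e.g., rinses, toothpastes, fluoride varnish) will be discontinued". Section III.B makes percent change in hypersensitivity, compared across the three groups, the primary analysis.

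**The concern.** The protocol accepts that recent use of an active product spoils the baseline, since it requires four weeks off desensitizing dentifrices. As worded, that protection covers the control type of product and not clearly the products under test. Yet the hypothesis in section I.A is that both test products reduce sensitivity more than the control does.

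If that hypothesis is right, a subject using Clinpro 5000 up to Visit 1 has a baseline VAS already lowered by it. Allocated to Clinpro, the subject continues the same product and has little further fall to show. Allocated to another arm, the subject's change mixes the effect of the new product with withdrawal of the old one. In neither case does percent change measure starting the assigned product. At stake is how to interpret the Clinpro-control contrast in a pilot meant to decide whether a larger trial is worthwhile.

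**Working it through.** **Which users does the wording reach?**

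| Product used before Visit 1 | Desensitizing dentifrice? | Varnish or precipitating solution? | Result |
|---|---|---|---|
| Sensodyne | Yes, by its stated approval | No | Excluded for four weeks |
| Clinpro 5000 | Not on the protocol's description (anti-caries) | No | Eligible |
| MI Paste Plus | Unclear: approved for hypersensitivity, but a finger-applied paste | No | Depends on the screener |

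Nothing else closes the gap. The rule on other hygiene products in III.D.3 is an on-study withdrawal rule. Other topical products stop only after the baseline reading. There is no run-in, and no procedure says that prior use of the test products is recorded.

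**The plan's own figure.** Inputs from III.B: mean improvements 5%, 30% and 30%, SD 25%, 10 per group, one-way ANOVA, alpha 0.05. The grand mean is 65/3 = 21.67.

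Noncentrality = 10 × [(5 − 21.67)² + 2 × (30 − 21.67)²] / 25² = 10 × 416.7 / 625 = 6.67, with 2 and 27 degrees of freedom.

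Power is 58.1%, against 58% stated. The figure reproduces and is not in dispute.

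**Illustration of the gap.** Assumptions, none of them from the documents:

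- A share p of every arm are current Clinpro users.
- A user allocated to Clinpro improves 5% instead of 30%.
- Other subjects follow the planned means.
- Let c be the mean percent improvement of Clinpro users allocated to control.

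Clinpro mean = 30(1 − p) + 5p. Control mean = 5(1 − p) + cp. Contrast = 25(1 − p) + (5 − c)p.

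*Case A, benefit persists after switching:* c = 5, so the contrast is 25(1 − p).

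*Case B, benefit fully lost on switching:* Clinpro had lowered VAS to 0.70 of its untreated level, and control brings it to 0.95 of that level. Then c = 100 × (1 − 0.95/0.70) = −35.7.

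| p | A: Clinpro − control | B: Clinpro mean | B: control mean | B: Clinpro − control |
|---|---|---|---|---|
| 0 | 25.0 | 30.0 | 5.0 | 25.0 |
| 5% | 23.75 | 28.75 | 2.96 | 25.8 |
| 10% | 22.5 | 27.5 | 0.93 | 26.6 |
| 20% | 20.0 | 25.0 | −3.14 | 28.1 |

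The contrast is unchanged when 5 − c = 25, that is c = −20. The sign of the shift thus turns on how much of the old benefit is lost after switching.

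**Power.** I widened each affected arm's variance for the mixture: 625 + p(1 − p) × (difference between user and non-user means)². In case A, omnibus power is about 53% at p = 10% and 48% at p = 20%. In case B, where MI Paste Plus-arm users have mean change 100 × (1 − 0.70/0.70) = 0, it is about 56% at both shares: the larger contrast is offset by extra spread.

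**Scale.** The standard error of a two-arm difference is 25 × √(2/10) = 11.2 points, so every shift above is well inside the trial's own noise.

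**The case against.** The strongest reply is that the harm is conditional and may be very small. It needs enrolled subjects who use the product, and no usage rate is given. The background says that "dental practitioners and sales representatives have promoted several anti-caries products", which is neither a prevalence nor a statement about Clinpro 5000 or MI Paste Plus in particular. Recruitment under III.N also reaches well beyond dental patients, through the medical and nutrition schools and online postings. The harm further needs Clinpro to affect sensitivity, which the protocol calls only anecdotal; if it has no effect, prior use leaves the baseline unchanged. Entry requires a VAS of at least 3, which removes users whose sensitivity has resolved. A recent or irregular user might still improve under the study regimen. All of this stands, and it limits the consequence rather than the reading of the exclusion.

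A second reply is that randomization balances prior users. It does so in expectation, but a user's response still depends on whether the allocated product is the same or new, so balance does not remove the problem. Nor is balance assured in small arms: with 6 users among 30 subjects at 10 per arm, the control and Clinpro arms differ by 2 or more with probability 41%.

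A reader might infer a net bias against the test products. The documents do not support that. It considers same-product subjects alone and holds control at 5%, leaving out withdrawal in switched subjects, which can push the contrast the other way. A reader might also infer that both test products are plainly let through. Only Clinpro 5000 is; a screener could reasonably treat MI Paste Plus, given its stated approval, as a desensitizing product.

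**Conclusion.** The gap in the eligibility wording is established from the text: recent users of the control type of product are washed out, current Clinpro 5000 users are eligible, and MI Paste Plus users fall in an unclear area. With no run-in, those admitted may bring an already treated baseline to a percent-change endpoint.

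The consequence cannot be quantified from the documents. Under the stated assumptions the planned 25-point contrast moves by −2.5 to −5 points or by about +1.6 to +3.1 points at user shares of 10% to 20%, and by little or nothing near zero prevalence. What is supported is a possible distortion of unknown direction and size. No figure in the plan is wrong. This is a worthwhile low-cost improvement, not a fault that invalidates the design.

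**What to change.** Extend the existing four-week exclusion in III.D.2 to any study product and its class. The line could read: used, within the preceding four weeks, a desensitizing dentifrice, Clinpro 5000 or another 5000 ppm fluoride dentifrice, or MI Paste, MI Paste Plus or another calcium-phosphate product. Ask about these products by name in the screening interview, questionnaire or script already planned in III.N, and record the answers.

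The cost is one eligibility line and one screening question, submitted as an IRB amendment. Some current users will be excluded or will enter later, which may slow recruitment slightly. The planned 10 evaluable subjects per group, the stated 58% power and the analysis are unchanged.

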- Teeth with carious lesions, buccal vertical cracks in enamel, evidence of irreversible pulpitis (pain lasting more than five seconds after air stimulation)
- Pregnant/ lactating patients (Clinpro5000 has 5000ppm fluoride and there is a risk of ingesting the product)
- Patients with Milk Allergy (CPP-ACP is a dairy based product)
- Patients on Kidney Dialysis (due to the free calcium in CPP-ACP, dialysis patients should be on a diet with limited calcium)

3) Subject Withdrawal/Termination Criteria

- Subjects will be withdrawn from the study if they report the use of other dental hygiene products, including but not limited to: toothpaste, rinses, fluoride varnishes

- Subjects will be withdrawn from the study if they undergo any phase I periodontal procedures, including a prophylaxis or scaling and root planing
- Subjects would be withdrawn if they experience a negative side effect from any product used in the study.
- The tooth being studied is extracted, damaged from trauma or receives endodontic therapy.
- Subjects may participate in another research study at the same time, as long as it does not impact the results from this study.
- Subjects who do not comply with the study procedures, such as not returning for visits, not using product as documented in diary, may be withdrawn from the study.
- Subjects who become pregnant during the course of the study will be withdrawn. Subjects will be informed in the informed consent form to inform principal investigator or their designate if they become pregnant.
- Subjects who decide to stop participating in the study will be withdrawn.

The Principal Investigator will determine whether subjects (either withdrawn subjects or subjects completing the study) are in need of additional treatment and/or follow-up observation as a result of participation in this trial.

E) Assessment

1) Risk

This study poses minimal risk to subjects as these are products that are approved for use.

With Clinpro5000, although the patient will be instructed not to ingest the product, ingestion may result in GI discomfort, nausea, vomiting, diarrhea, cramping and fluorosis in children. Fluoride exposure should be monitored in pregnant and nursing women. Pregnant and lactating women and children will be excluded from this study.

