Responsible for ongoing communication with the IRB – PI

Obtaining informed consent – PI, Co-Is, and study coordinator (who is GCP and CITI trained)

Maintaining study records – PI

Sensitivity testing and oral exam – PI and Co-Is

Product distribution and instructions, answering any questions that the subject has regarding the products. – Study coordinator (with instruction from PI/Co-I who has not treated subject).

Reviewing and collecting the patient's diary, handing out diaries - PI, study coordinator/team member

Intraoral photographs – PI, Co-Is

Gift card distribution – PI, study coordinator/team member

5) Payment for Participation

(a) Compensation

The subject will be given up to \$100 in gift cards. \$25 upon completion of visit 1, \$25 upon completion of visit 2, \$25 upon completion of visit 3, \$25 upon completion of visit 4.

(b) Transportation

No reimbursement will be given for transportation or parking

(c) Payment and Insurance

There will be no fees associated with the study procedures. Neither the subject, nor their insurance company, will be billed for any study procedures.

6) Study Results

If interested, a copy of the published paper will be mailed to interested study participants. A log will be kept of the participants who are interested in receiving study results.

7) Confidentiality

(i) To ensure confidentiality of subject information, each subject enrolled in the study will be assigned a unique alphanumeric code. Subjects' files will be kept in a secure, locked cabinet in a secure room (DHS-1418) when the files are not reviewed. The information will only be shared between the researchers. All HIPAA requirements will be followed. All electronic files will be kept on a password protected computer in a secure, locked office.

(a) Coding

(i) Each will be assigned a subject identification number. Alphanumeric identification numbers will be assigned sequentially. The full subject identification number will consist of the three letters from the subject's initials and their enrollment number. This will be accessible by study personnel only.

(b) Access / Data Safety Monitoring Board

Only study personnel will have access to data. Investigators will permit monitoring, audits, and regulatory inspections and will provide direct access to study related documentation.

10) Data Safety Monitoring Plan:

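### The withdrawal list does not separate stopping a product from leaving the study, so testable subjects get no further sensitivity scores and the comparison can be biased in either direction

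*Combined protocol and SAP*

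**What the plan says.** Section III.D.3 (Subject Withdrawal/Termination Criteria) is one list with one consequence. The entries that matter here are:

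- Side effects: "Subjects would be withdrawn if they experience a negative side effect from any product used in the study". No severity is given.
- Other products: "Subjects will be withdrawn from the study if they report the use of other dental hygiene products". Toothpastes, rinses and fluoride varnishes are the examples.
- Dental procedures: "Subjects will be withdrawn from the study if they undergo any phase I periodontal procedures, including a prophylaxis or scaling and root planing".
- Tooth events: "The tooth being studied is extracted, damaged from trauma or receives endodontic therapy".
- Non-compliance: "Subjects who do not comply with the study procedures, such as not returning for visits, not using product as documented in diary, may be withdrawn". This entry is discretionary and has no threshold.

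Section III.F (Study Procedures) fixes the order of Visits 2, 3 and 4. A study team member first asks about history, compliance, adverse events and the diary. The eligibility and withdrawal criteria are then reviewed to confirm that the subject still qualifies, and only after that does the examiner collect the sensitivity data.

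The only provision for withdrawn subjects is at the end of III.D.3, where the Principal Investigator judges whether more treatment or follow-up observation is needed. No VAS or Schiff assessment is attached to it.

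Section III.B (Sample Size and Statistical Analysis) compares percent change between the three groups without naming a visit, and drops the information of patients lost to follow-up. It defines no all-randomized analysis set, no imputation and no sensitivity analysis. Section III.H.5 pays $25 for each completed visit.

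**The concern.** A subject who attends Visit 2 and reports a mild reaction, or one use of another toothpaste, can be examined that day and at week 8. Followed as written, the protocol removes this subject before the tooth is tested. Values that are never collected cannot be restored by a later choice of analysis.

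The loss need not be neutral between arms. Group II uses two products, one of them applied by finger. The gastrointestinal effects of ingestion are listed for Clinpro 5000 only. A subject with persisting pain has more reason to try something else, and the protocol's own Alternatives section lists other remedies for sensitivity. The discretionary entry adds judgement: the examiner is blinded, but nothing says that whoever decides on withdrawal for non-compliance is. A subject who reports another product may also forgo payment for visits not completed, which discourages candid reporting.

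If loss is related to arm or response, the subjects left at Visit 4 are no longer the groups that were randomized. This pilot is meant to decide whether a larger study is needed, so both the estimated difference and the reasons for leaving each product matter.

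**Working it through.** **Inputs, all from III.B.** Mean improvement is about 5% for control and about 30% for each test group, with a common SD of 25. There are 10 evaluable subjects per group, up to 13 recruited, and alpha is 0.05. Positive change means improvement. The documents give no withdrawal rates, so every withdrawal fraction below is an assumption.

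**1. The plan's own figures.** For one-way ANOVA the noncentrality is n × Σ(μᵢ − μ̄)²/SD². The overall mean is 21.67, and the squared deviations are 277.8 + 69.4 + 69.4 = 416.7. So λ = 10 × 416.7/625 = 6.667 with 2 and 27 df, which gives power of 58.1%, matching the stated 58%. The recruitment target also fits: 10/0.80 = 12.5, rounded up to 13. The allowance is 3/13 = 23.1%. It replaces numbers but does not correct selective loss.

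**2. Withdrawal of subjects who do not improve.** Suppose a fraction w of subjects with change below 0 is withdrawn. With p = Φ(−μ/σ) and E = μp − σφ(μ/σ), the remaining mean is (μ − wE)/(1 − wp).

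- Control: p = 0.4207, E = 5 × 0.4207 − 25 × 0.3910 = −7.672.
- Test: p = 0.1151, E = 30 × 0.1151 − 25 × 0.1942 = −1.403.
- At w = 0.5, control loses 21% and its mean becomes 8.836/0.7896 = 11.19. Each test arm loses 6% and its mean becomes 30.701/0.9425 = 32.58. The difference is 21.39 instead of 25.

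| w | Control mean | Test mean | Difference |
|---|---|---|---|
| 0.3 | 8.36 | 31.51 | 23.15 |
| 0.5 | 11.19 | 32.58 | 21.39 |
| 0.7 | 14.70 | 33.70 | 19.00 |
| 1.0 | 21.88 | 35.49 | 13.61 |

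**3. Selective loss from one arm only.** If a fraction w of below-mean responders leaves one arm, its mean rises by wσφ(0)/(1 − w/2). At w = 0.5 this is 0.5 × 25 × 0.3989/0.75 = 6.65 points, with 25% of the arm lost. At w = 0.3 it is 3.52 points and at w = 0.7 it is 10.74.

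**4. Loss within the 13 recruited.** If k of 13 subjects are lost and would have done d points worse than those remaining, the arm mean is too high by (k/13)d. For d from 10 to 30, one loss gives 0.8 to 2.3 points and three losses give 2.3 to 6.9.

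**5. Extreme bound.** Suppose the three products are truly equal, each test arm loses its k worst responders, and control loses k at random. In simulation (40,000 trials) the spurious difference is about 3.5, 6.4 or 9.2 points for k = 1, 2 or 3, and the ANOVA false-positive rate is 8.2%, 12.7% or 18.7%. Random loss leaves it at about 5%. This is a ceiling for these losses, not a forecast.

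Step 2 shrinks the difference. Steps 3 and 5 can create or enlarge one.

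**The case against.** The strongest reply is that withdrawing users of other products keeps the comparison on-product, which is what the hypothesis is about, and that retaining them may not help. Take step 2 at w = 0.5 and keep the switchers' later scores. If the other product brings them to a 5% improvement, the difference is 21.1 points; at 15% it is 19.6; at 30% it is 17.3 (assumed values). Withdrawal gives 21.4. This stands as a limit on any single analysis. It does not favour discarding the data: with the scores collected, both the all-randomized and the on-product comparison can be shown, and without them only the second is possible.

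Scale also counts. With 10 per group the standard error of a pairwise difference is 25 × √(2/10) = 11.2 points, and the central shift in step 2 is under 4. The plan states its 58% power openly and calls itself a pilot. That is a reason to treat this as an improvement and not as a fatal flaw.

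A reader might infer more than the documents support:

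- **That subjects are removed because the product failed.** Lack of efficacy is not a listed criterion. The route through other products is an inference, and a prophylaxis or trauma need not relate to the product at all.
- **That the side-effect rule itself produces the shifts above.** The illustrations model response-related loss. No side-effect rates are given, and no section links side effects to VAS response.
- **That a specified week 8 primary outcome is lost.** No primary visit is named. Week 8 is simply the last visit, and earlier scores may exist.
- **That withdrawn subjects are expressly excluded from analysis.** The exclusion sentence concerns loss to follow-up. Exclusion is the natural result when there is no later score, but it is not stated. The side-effect entry likewise says only that subjects are withdrawn; leaving the study is explicit in neighbouring entries and implied by the visit check.
- **That subjects with a reaction go unmonitored.** The Principal Investigator must judge their need for follow-up, and all adverse events are to be recorded. Only the scheduled assessments are not continued.

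**Conclusion.** The point holds as a risk. The plan does not separate stopping product from leaving the study, and it schedules no sensitivity score after withdrawal for subjects who could generally still be tested. An extracted tooth is the clear exception, and subjects who do not return are not available in any case.

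The comparison can be biased in either direction; the documents do not show that it is distorted. Under the plan's means and SD, and normally distributed change, withdrawing half of those with change below 0 moves the difference from 25 to about 21 points. Losing half of the below-average responders from one arm moves that arm by about 6.65 points. Both fractions are assumptions, and the true size and direction depend on withdrawal rates by arm that are not known. This is a cheap improvement.

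**What to change.** Change data collection and analysis only. Leave the rules on when product is stopped exactly as they are, including those that are mandatory.

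- In III.D.3 and III.F, for a subject who meets a withdrawal trigger, still consents and has a study tooth that can be tested, record the event, its date and the reason. Continue the scheduled VAS, Schiff and adverse event assessments, with the visit payment, through Visit 4.
- In III.B, analyse all randomized subjects with available values in their assigned arm, show an on-product analysis alongside, and report withdrawals by arm and reason.

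The cost is an IRB amendment and a few visits that are already planned.

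The statistical downside is that scores after use of another product may dilute or mask product differences, which is why the on-product analysis is also shown. Power may move either way. If all 13 per group are followed and respond as the plan assumes, it is 71.6%. If 1, 2 or 3 of 13 in each test arm improve only 5% (assumption), the all-randomized difference is 25 × (1 − k/13) = 23.1, 21.2 or 19.2 points, with simulated power of about 61%, 52% or 42%. Dropping those subjects would still show 25 points, with power of about 70%, 68% or 66%.
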